2.2. Background

Gepotidacin has demonstrated clinical efficacy in a Phase II study for acute bacterial skin and skin structure infections, and in a Phase II study for gonorrhea.

A detailed description of the chemistry, pharmacology, efficacy, and safety of gepotidacin is provided in the Investigator's Brochure [GlaxoSmithKline Document Number [CM2010/00033/06](#)].

2.3. Benefit/Risk Assessment

Summaries of findings from both clinical and nonclinical studies conducted with gepotidacin can be found in the Investigator's Brochure. The following section outlines the risk assessment and mitigation strategy for this protocol.

2.3.1. Risk Assessment

Potential Risk of Clinical Significance	Summary of Data/Rationale for Risk	Mitigation Strategy
Investigational Product (IP) Gepotidacin		

Gastrointestinal (GI) Effects
 
Based on nonclinical data, gastrointestinal effects were mild ulceration of the nonglandular mucosa and minimal erosion and/or mural inflammation of the glandular mucosa in stomach (rat, oral study); moderate cecal ulceration and minimal colonic erosion (rat, IV study); and vomiting (dog). Lower gastrointestinal effects (soft stools, flatulence, and diarrhea) are among the most common AEs reported in gepotidacin clinical studies.
	
Gastrointestinal effects observed in gepotidacin clinical studies, both Phase I studies and the Phase II ABSSSI study, included diarrhea (very common, ≥10%) and flatulence (common; ≥1% and <10%); all nonserious and mild in severity (see Section 6 of the Investigator's Brochure).
 
In the Phase II urogenital gonorrhea study, the most frequently reported gastrointestinal AEs overall were diarrhea, flatulence, abdominal pain, and nausea. Comparing the treatment groups, the incidence of diarrhea and nausea was higher in the 3000-mg treatment group and incidence of flatulence was higher in the 1500-mg treatment group.
 
Few occurrences of Clostridium difficile have been reported in clinical studies (see Section 6 of the IB). Of the 282 healthy participants in Phase I studies who have received gepotidacin, C. difficile was reported in 8 participants, including 2 elderly participants in association with soft stools or diarrhea. In the Phase I renal impairment and hepatic impairment studies and in the Phase II ABSSSI, urogenital gonorrhea, and uUTI studies, no cases of C. difficile-associated diarrhea were reported.
	
Exclusion criterion and close monitoring of clinical parameters and AEs will be conducted to mitigate and assess GI effects.
 
Suspected C. difficile infection will be managed according to a prespecified algorithm provided in Appendix 7.
 
Participant evaluation criteria: Participants experiencing Grade 3 or Grade 4 AEs will be followed as appropriate until resolution of the AE (see Section 7.1.3).

Potential Risk of Clinical Significance	Summary of Data/Rationale for Risk	Mitigation Strategy

Cardiovascular Effects Reversible increase in QT prolongation and a mild increase in heart rate in human participants.
	
In Study BTZ115775 (see GSK Document Number 2015N227098_00 Study ID BTZ115775), the infusion of gepotidacin at a dose of 1000 mg and 1800 mg over 2 hours caused a mild heart rate effect of approximately 6 bpm to 10 bpm and a QT prolongation, measured as $\Delta\Delta\text{QTcF}$, of 12 msec to 22 msec. The QT prolongation evolved during the infusion and was quickly reversed over 2 hours after the end of the infusion. Blood pressure observations were within normal ranges.
 
No changes in QRS or QTc of clinical concern have been seen in the clinic (Phase I studies, including renal impairment and hepatic impairment studies, and Phase II ABSSSI and uUTI [acute cystitis] studies) (see Section 6 in the IB). There were electrocardiographic changes noted in a Phase I hepatic impairment study. The majority of participants with severe hepatic impairment had both predose and maximum postdose ECG parameter QTcB and QTcF values of <450 to \leq479 msec throughout the study. Cardiovascular events reported in the Phase II urogenital gonorrhea study were ECG ST segment elevation and palpitations (1 participant each) in the 1500-mg treatment group and tachycardia (1 participant) in the 3000-mg treatment group.
	
Exclusion criteria, close monitoring of clinical parameters, and AEs will be conducted and stopping criteria will be utilized to mitigate and assess cardiovascular effects.
 
Note: Participants with baseline QTcF interval >450 msec will be excluded.
 
Participant monitoring criteria: Participants experiencing a QTcB and/or QTcF >500 msec and/or a change from baseline in QTc >60 msec (see Section 7.1.2).


Acetylcholinesterase (AChE) Inhibition In a mass spectrometry model performed with gepotidacin, AChE was inhibited with a concentration of inhibitor where the response (or binding) was reduced by half (inhibitory concentration) of approximately 5 $\mu\text{g/mL}$ (7.5 $\mu\text{g/mL}$ of total drug concentration).
	
At higher doses, some participants have experienced effects consistent with increased cholinergic tone, including central nervous system and GI effects (increased salivation, slurred speech, blurred vision, dizziness, light-headedness, and GI upset). These effects appear to be related to C_{max} and are significantly attenuated when C_{max} is below 14 $\mu\text{g/mL}$.
	
Coadministration of anticholinergics and administration in participants with certain concomitant conditions will be excluded.
 
Close monitoring of clinical parameters and AEs will be conducted to assess effects potentially related to AChE inhibition. The C_{max} is expected to be below 14 $\mu\text{g/mL}$ in this study.

Potential Risk of Clinical Significance	Summary of Data/Rationale for Risk	Mitigation Strategy
Rash/Hypersensitivity	
A fine, mild, generalized pruritic macular skin rash was seen in 3 of 6 participants following 10 days of dosing 1500 mg 3 times daily (see GSK Document Number 2014N198291_00 Study ID BTZ115198).
 
Rash was reported as an AE for 4 of 122 participants (3%) and consisted of mild, related urticaria; moderate, related rash maculopapular; mild, related rash; mild, related urticaria; and mild, not related arthropod bite (see GSK Document Number 2015N243789_00 Study ID BTZ116704).
 
There has been no other evidence of hypersensitivity in human participants to date.
	
Exclusion criterion: History of sensitivity to any of the study drugs, components thereof, or a history of drug or other allergy that, in the opinion of the investigator or GlaxoSmithKline medical monitor, contraindicates their participation.
 
Participant monitoring: Participants will be monitored closely for cutaneous effects throughout the study, and specialist advice will be sought as needed to evaluate any clinically significant finding.
 
Participant evaluation criteria: Grade 3 or higher rash or Grade 2 rash with evidence of systemic involvement (see Section 7.1.4).

bpm = beats per minute; ABSSSI = acute bacterial skin and skin structure infection; AE = adverse event; C_{max} = maximum concentration; ECG = electrocardiogram; IB = Investigator's Brochure; IV = intravenous; $\Delta\Delta$ QTcF = placebo-corrected change-from-baseline in corrected QT interval using the Fridericia formula; QTc = corrected QT interval; QTcB = QT interval corrected for heart rate according to Bazett; QTcF = interval corrected for heart rate according to Fridericia; uUTI = uncomplicated urinary tract infection.

2.3.2. Benefit Assessment

Since this Phase I study is being conducted in healthy adult and adolescent participants, there is no direct clinical benefit to study participants. Participation in this study will contribute to the process of developing new antibiotic therapies in areas of growing unmet need.

2.3.3. Overall Benefit: Risk Conclusion

The risk of AEs is minimized for the populations being investigated in the proposed study by careful selection of dose and participants for the study, the relatively short duration of study drug exposure, and the extent of safety monitoring incorporated into the study.

3. OBJECTIVES AND ENDPOINTS

Objectives	Endpoints
Primary	
Part 1 
 To evaluate the pharmacokinetics of a single 1500-mg dose and two 3000-mg doses of gepotidacin given 6 and 12 hours apart in adult participants 	1500 mg Single Dose 
 Plasma gepotidacin AUC(0-t), AUC(0-∞), AUC(0-24), AUC(0-48), and Cmax, as data permit 3000 mg Two Doses 
 Plasma gepotidacin AUC(0-t), AUC(0-τ), AUC(0-24), AUC(0-48), Ro (accumulation ratio), and Cmax, as data permit
Part 2 
 To evaluate the pharmacokinetics of a single 1500-mg dose and two 3000-mg doses of gepotidacin given at a dosing interval (to be determined) in adolescent participants 	1500 mg Single Dose 
 Plasma gepotidacin AUC(0-t), AUC(0-∞), AUC(0-24), AUC(0-48), and Cmax, as data permit 3000 mg Two Doses 
 Plasma gepotidacin AUC(0-t), AUC(0-τ), AUC(0-24), AUC(0-48), Ro (accumulation ratio), and Cmax, as data permit
Parts 1 and 2 
 To assess the safety of gepotidacin in adult participants and adolescent participants 	
 Adverse events, clinical laboratory tests, vital signs (systolic and diastolic blood pressure and heart rate), and 12-lead electrocardiogram readings

Objectives	Endpoints
Secondary	

Part 1
 
 To assess the urine pharmacokinetics of gepotidacin following a single 1500-mg dose and two 3000-mg doses of gepotidacin given 6 and 12 hours apart in adult participants 
Part 2
 
 To assess the urine pharmacokinetics of gepotidacin following a single 1500-mg dose and two 3000-mg doses of gepotidacin given at a dosing interval (to be determined) in adolescent participants 
Parts 1 and 2
 
 To assess the plasma pharmacokinetics of gepotidacin 	
 Urine endpoints include Ae total, Ae(t1-t2), AUC(0-τ), AUC(0-24), AUC(0-48), fe%, and CLr of gepotidacin, as data permit Urine endpoints include Ae total, Ae(t1-t2), AUC(0-τ), AUC(0-24), AUC(0-48), fe%, and CLr of gepotidacin, as data permit Plasma gepotidacin Tmax, tlag, and t1/2, as data permit

4. STUDY DESIGN

4.1. Overall Design

This is a Phase I, double-blind, single-center, randomized, sequential, two-part study. Part 1 is being conducted to evaluate the PK of the gepotidacin tablets in healthy adult participants. Part 2 will evaluate the PK of the gepotidacin tablets in healthy adolescent participants.

Part 1: Pharmacokinetics in Healthy Adult Participants

Part 1 is a 3-period, fixed-sequence study that will assess the PK of a single 1500-mg dose (Period 1) and two 3000-mg doses of gepotidacin at Hours 0 and 12 (Period 2) and Hours 0 and 6 (Period 3) in healthy adult participants.

Participants will be randomly assigned to receive either all active treatment (gepotidacin) or placebo for all 3 periods. Approximately 17 participants will be randomized (in a 14:3 ratio) to receive a single dose of gepotidacin 1500 mg (Treatment A) or matching placebo (Treatment B) in Period 1, gepotidacin 3000 mg separated by 12 hours (Treatment C) or matching placebo (Treatment D) in Period 2, and gepotidacin 3000 mg separated by 6 hours (Treatment E) or matching placebo (Treatment F) in Period 3 to obtain 12 evaluable participants on active treatment and 2 evaluable participants on placebo.

Participants will participate in 3 treatment periods, and blood and urine samples will be collected for PK analysis of gepotidacin concentrations according to the Schedule of Activities (SoA; see Section 1.3).

This will be a two-part study in which the PK and safety data will be reviewed after completion of Part 1 before enrolling participants into Part 2. The dosing interval in Part 2, Period 2 will be based on the PK, safety, and tolerability data from Part 1.

Part 2: Pharmacokinetics in Healthy Adolescent Participants

Part 2 is a 2-period, fixed sequence study that will assess the PK of a single 1500-mg dose (Period 1) of gepotidacin and two 3000-mg doses (Period 2) of gepotidacin in healthy adolescent participants. The two 3000-mg doses will be separated by a time interval that will be determined based on data from Part 1. The number of PK samples and the PK sampling time points may be modified based on the adult PK data from Part 1.

Participants will be randomly assigned to receive either all active treatment (gepotidacin) or placebo for both periods. Approximately 17 participants will be randomized (in a 14:3 ratio) to receive a single dose of gepotidacin 1500 mg (Treatment A) or matching placebo (Treatment B) in Period 1 and gepotidacin 3000 mg (Treatment G) or matching placebo (Treatment H) in Period 2 to obtain 12 evaluable participants on active treatment and 2 evaluable participants on placebo.

The interval for the two 3000-mg doses in Period 2 will be between 6 hours and 12 hours based on the PK and safety results from Part 1.

Participants will participate in 2 treatment periods, and blood and urine samples will be collected for PK analysis of gepotidacin concentrations according to the SoA (see Section 1.3).

For Part 2 only, there may be a 7-day interval between doses in Period 1 and Period 2 to accommodate the adolescent population school schedule. Treatment Period 1 and Treatment Period 2 may be separated by no more than 10 days.

4.2. Scientific Rationale for Study Design

Although total daily oral 6000 mg doses have been given to healthy participants and patients as 2000 mg TID for up to 14 days and daily IV 4500 mg (equivalent to 9180 mg oral dose and based on absolute bioavailability of 46%) doses have been given to healthy participants as TID regimen for up to 10 days, the safety and PK of two 3000 mg doses given either 6 or 12 hours apart have not been characterized previously and gepotidacin has not been administered previously to adolescents; this study will support inclusion of adolescents with a body weight ≥ 40 kg in future Phase III studies and will provide the safety and PK data of two 3000 mg doses separated by the selected dose intervals in Part 1 and Part 2.

Both adult and adolescent (≥ 12 to < 18 years of age) eligible participants will be enrolled in this double-blinded study. Adolescent participants will only be enrolled if allowed per the study site's IRB and national regulatory guidelines, and enrollment will be contingent upon such approvals. Adolescent assent forms and adult consent forms will be developed with oversight from local governing IRB (see [Appendix 3](#)).

Part 1 is being conducted to evaluate the pharmacokinetics, safety, and tolerability of the gepotidacin tablet.

Part 2 will evaluate the pharmacokinetics, safety, and tolerability of the gepotidacin tablet in adolescent participants. Testing gepotidacin in this specific population will provide PK, safety, and tolerability information needed for their inclusion in future pivotal Phase III studies.

4.3. Justification for Dose

Selection of dose and dosing frequency for this study is justified based on observed safety efficacy and PK data following single oral dosing (1500 to 3000 mg), repeat oral twice daily (BID; 1500 to 2300 mg) and TID dosing (1500 to 2000 mg) in previous studies. In addition, exposures higher than anticipated in this study were achieved following single IV dosing of 1800 mg equivalent to an oral dose of 3913 mg (absolute bioavailability is 46%) and repeat IV dosing of 1500 mg TID for 10 days (equivalent to an oral daily dose of approximately 9180 mg).

Based on PK modeling, gepotidacin will be administered for gonorrhea as two single oral 3000-mg doses, given either 6 or 12 hours apart with a minimum body weight of 40 kg, to provide higher daily systemic exposures that allow coverage of *Neisseria gonorrhoeae* isolates with higher gepotidacin MIC values, which are likely to be observed in the global Phase III study and reduce the risk of resistance emergence. Less than 3% of the population is expected to exceed the C_{max} threshold of 14 $\mu\text{g/mL}$.

In the current study, gepotidacin will be administered as a single oral 1500-mg dose and 2 oral 3000-mg doses. The two 3000-mg doses, given either 6 or 12 hours apart in Part 1 and at the selected dose interval in Part 2, compared with the single 1500-mg dose, are expected to provide valuable PK and safety data to guide Phase III studies and the prescribing information for the gepotidacin tablet.

4.4. End of Study Definition

A participant is considered to have completed the study if he/she has completed all phases of the study including the final date on which data were or are expected to be collected.

The end of the study is defined as the date of the last visit of the last participant in the study or last scheduled visit shown in the SoA (see [Section 1.3](#)) for the last participant in the study.

5. STUDY POPULATION

Prospective approval of protocol deviations to recruitment and enrollment criteria, also known as protocol waivers or exemptions, is not permitted.

If participants prematurely discontinue the study, additional replacement participants may be recruited at the discretion of the sponsor in consultation with the investigator.

Replacement participants will be assigned to the same randomization sequence as the participant who discontinued.

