6.3. Measures to Minimize Bias: Randomization and Blinding

This is a double-blind study. The study treatment taken during the study will be double-blind. An unblinded pharmacist will dispense study intervention. Neither the participant nor immediate study personnel (i.e., investigators, PPD staff) will know which study treatment the participant is receiving. Participants who are randomly assigned to receive placebo will receive a matching placebo form of the active treatment. The matching placebos will look identical to the active form.

In case of an emergency, the investigator has the sole responsibility for determining if unblinding of a participant's treatment assignment is warranted. Participant safety must always be the first consideration in making such a determination. If the investigator decides that unblinding is warranted, the investigator should make every effort to contact GSK prior to unblinding a participant's treatment assignment unless this could delay emergency treatment of the participant. If a participant's treatment assignment is unblinded, GSK must be notified within 24 hours after breaking the blind. The date and reason that the blind was broken must be recorded in the source documentation and electronic case report form (eCRF), as applicable.

In Part 1 and Part 2, participants will be randomized in a 14:3 ratio to receive study intervention. Investigators will remain blinded to each participant's assigned study intervention throughout the course of the study.

Unblinded monitors and in the event of a quality assurance audit, the auditor will be allowed access to unblinded study intervention records at the site to verify that randomization/dispensing has been done accurately.

A participant will be withdrawn if the participant's intervention code is unblinded by the investigator. The primary reason for discontinuation (the event or condition which led to the unblinding) will be recorded in the eCRF.

To protect the safety of participants, GSK safety medical monitor may remain unblinded to participant treatment throughout the study and will monitor safety data in real time.

Limited members of GSK staff (e.g., statistician, pharmacokineticist, and medical monitor) will be unblinded to study treatment at the end of Part 1 in order to determine which dosing frequency to take forward to Part 2.

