GSK's Global Clinical Safety and Pharmacovigilance (GCSP) staff may unblind the intervention assignment for any participant with an SAE. If the SAE requires that an expedited regulatory report be sent to one or more regulatory agencies, a copy of the report, identifying the participant's intervention assignment, may be sent to investigators in accordance with local regulations and/or GSK policy.

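### If the sponsor replaces a participant whose code the investigator has broken, the same-sequence rule can reveal the newcomer's arm before the first dose

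*Protocol*

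**What the plan says.** Four rules in the protocol bear on this.

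- **Replacement (Section 5).** When someone stops early, "additional replacement participants may be recruited at the discretion of the sponsor in consultation with the investigator". The assignment rule has no exception: "Replacement participants will be assigned to the same randomization sequence as the participant who discontinued".
- **What a sequence is (Section 4.1).** For Part 1: "Participants will be randomly assigned to receive either all active treatment (gepotidacin) or placebo for all 3 periods". For Part 2: "Participants will be randomly assigned to receive either all active treatment (gepotidacin) or placebo for both periods". The order of periods is fixed.
- **Code breaks (Section 6.3).** "A participant will be withdrawn if the participant's intervention code is unblinded by the investigator". Separately, sponsor safety staff may unblind a participant with an SAE, and where an expedited regulatory report is needed, a copy "identifying the participant's intervention assignment, may be sent to investigators".
- **Blinding (Section 6.3).** "Investigators will remain blinded to each participant's assigned study intervention throughout the course of the study". The allocation is also given there: "In Part 1 and Part 2, participants will be randomized in a 14:3 ratio to receive study intervention". An unblinded pharmacist dispenses.

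SAP Section 10.5.1 says only that withdrawn participants may be replaced. Neither document treats an unblinded participant differently for replacement, provides reserve assignments, or says that the link between the leaver and the newcomer is kept from the investigator.

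**The concern.** A code break obliges withdrawal, withdrawal opens a place, and the rule for filling that place carries over the arm that the investigator has just learned. The protocol's own procedures can therefore undo its blinding commitment for the newcomer, for all three periods in Part 1 or both in Part 2.

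Safety is a primary objective in both Parts (Protocol Section 3). The investigator grades AE intensity and judges causality (Protocol Section 10.4.3). Those grades are added up into the acetylcholinesterase-inhibition Cumulative Grade (SAP Section 8.2.1), which has its own table and figure (SAP Table 2.6 and Figure 2.2). Part 1 safety results also help to choose the Part 2 dosing interval (Protocol Section 9.5). With only three placebo participants planned per Part, one assessment made with the arm known is a visible fraction of the comparator.

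**Working it through.** **1. The plan's precision figure.** Protocol Section 9.2 gives the distance from the upper 95% limit to the geometric mean at n = 12 as 14.5% for AUC(0-∞) (CV 21.5%) and 28.0% for Cmax (CV 40.3%). The formula is exp[t(0.975, n−1) × √ln(1+CV²) / √n] − 1, with t(0.975, 11) = 2.201.

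- AUC(0-∞): exp(2.201 × 0.2126 / √12) − 1 = 14.46%.
- Cmax: exp(2.201 × 0.3879 / √12) − 1 = 27.95%.

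Both reproduce. The point does not challenge them; they matter only for the cost of the fix.

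**2. Sequence equals arm.** SAP Section 2.3 lists A/C/E or B/D/F for Part 1, and A/G or B/H for Part 2. With two sequences per Part, one all active and one all placebo, naming the sequence names the arm.

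**3. The rules side by side.**

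- The investigator breaks a code: the arm is known and the participant is withdrawn (Section 6.3).
- The sponsor may replace, consulting the investigator (Section 5).
- If it does, the newcomer gets the same arm (Sections 5 and 4.1).
- The study is single-center (Section 4.1), so the site that learned the code assesses the newcomer.
- The investigator is meant to be blind to that newcomer (Section 6.3).

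The last line fails if the sponsor replaces and the investigator knows which departure the newcomer fills.

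**4. What the investigator would know.** Blind, the allocation alone gives 14/17 = 82.4% active and 3/17 = 17.6% placebo. With a known arm and a known link, there is no uncertainty left.

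**5. Share of the data affected.** The Safety population is everyone who took at least one dose (Protocol Section 9.3, SAP Section 4), and a withdrawn participant's available data stay in the summaries (SAP Section 10.5.1). If the withdrawn participant had been dosed, the replacement adds one to the arm:

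- placebo: 3 + 1 = 4, share 1/4 = 25%;
- active: 14 + 1 = 15, share 1/15 = 6.7%.

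If that participant was never dosed, the shares are 1/3 = 33% and 1/14 = 7.1%.

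**6. How often.** The documents give no code-break rate. Assuming a rate p per participant, the chance of at least one break among n is 1 − (1 − p)^n.

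| Assumed p | n = 17 (one Part) | n = 34 (both Parts) |
|---|---|---|
| 1% | 15.7% | 28.9% |
| 2% | 29.1% | 49.7% |
| 5% | 58.2% | 82.5% |

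At a given p these are ceilings. They count any break by any route, not a break followed by a replacement whose link is known.

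**7. Margin.** The plan randomizes 14 and 3 to obtain 12 and 2 evaluable (Section 4.1). The spare is 14 − 12 = 2 active and 3 − 2 = 1 placebo.

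**The case against.** The case for leaving the text alone is reasonable. Replacement is optional, so the sponsor can decline to replace a code-broken participant under the present wording. The margin in step 7 means that two active losses or one placebo loss need no replacement. Section 5 has the investigator consulted about recruiting; it does not say that the link is disclosed, and several replacements at once could blur it. No hypothesis is tested and safety is descriptive (Protocol Sections 9.1 and 9.4.2). PK, laboratory, ECG and vital-sign results are measured, laboratory grades are assigned by program (SAP Section 8.3), and AE intensity follows published toxicity tables.

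All of this stands and limits the size of the point. It does not remove the conflict: discretion not to replace is no instruction, and nothing written conceals the link.

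Three stronger readings are tempting and not supported:

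- **That an expedited SAE report also forces the participant out.** The withdrawal rule in Section 6.3 covers unblinding by the investigator only. The report route matters only if that participant discontinues for some reason and is replaced.
- **That unblinding of the newcomer is certain once a code is broken.** It also needs a decision to replace, a newcomer enrolled in that place, and knowledge of the link, which is an inference from consultation and the single site.
- **That every replacement needs concealment.** Where no assignment has become known to blinded staff, taking over the same sequence reveals nothing.

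**Conclusion.** The gap is real and narrow. As written, the replacement, withdrawal and blinding rules conflict when a participant whose code the investigator broke is replaced.

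The conclusion assumes that the sponsor chooses to replace and that the investigator knows whom the newcomer replaces. The effect is confined to one participant in a Part, at the shares in step 5, and mainly to AE severity and causality where these are matters of judgement. That the event is uncommon is itself a judgement, because the documents give no rate. The impact is modest and no planned precision figure is wrong, but the repair is cheap enough to be worth making before it is needed.

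**What to change.** Add one sentence to Protocol Section 5: a participant whose assignment has become known to blinded site staff is either not replaced, or is replaced by a newly randomized participant whose assignment comes from a reserve list held by the unblinded pharmacist, not from the same sequence. Wording it by who knows the assignment covers both the code break and the SAE report. Other replacements can stay under the present rule.

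The cost is that sentence and a short reserve list. The downside is that the affected arm may finish with one fewer evaluable participant. If the reserve list keeps the 14:3 ratio (an assumption), a departed placebo participant would be followed by another placebo only 3/17 = 17.6% of the time, so the placebo group would usually finish one short of its planned three. The margin of two active and one placebo covers one such loss unless other losses have already used it. If active numbers did fall from 12 to 11, precision would lie between the plan's own columns for n = 10 (16.4% and 32.0%) and n = 12 (14.5% and 28.0%).
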